## RESEARCH PROTOCOL AND STATISTICAL ANALYSIS PLAN

TITLE	The Effect of Balance Bike Training on Balance, Physical Activity Levels, and Participation in Children and Youth with Down Syndrome: A Pilot Study
ABSTRACT	
Background: Children with Down syndrome (DS) present with hypotonia, impaired balance and poor gross motor proficiency which lead to difficulty learning new motor skills, decreased engagement in physical activity, and limited participation in home, school, and community activities. Bicycle riding is a popular childhood activity with multiple health benefits; however, children with DS often have difficulty learning to ride a standard two-wheel bike. Purpose: The purpose of this pilot study is to determine the effectiveness of the Strider “Learn to Ride” intervention when used to teach children with DS to ride a two-wheel balance bike. Additional purposes include examining the immediate effects of the five-day “Learn to Ride” intervention on the balance of children with DS and the long-term effects of completion of the intervention on the participation and physical activity levels of children with DS. Methods: An estimated 20 children between the ages of 5 and 17 years old will be recruited to participate in the quasi-experimental, pre-post-test group design study. The participants will complete the five-day Strider “Learn to Ride” intervention under the instruction of a pediatric physical therapist. The immediate effects of the intervention on distance cycled and balance, using the Pediatric Balance Scale (PBS), will be assessed. Participation and physical activity levels will be assessed at long term follow-up using the Participation and Environment Measure for Children and Youth (PEM-CY) and a parent-report questionnaire.

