PURPOSE	The purpose of this pilot study is to determine the effectiveness of the Strider “Learn to Ride” intervention on the balance of children with Down syndrome and the long-term effects of completion of

	
the intervention on the participation and physical activity levels of children with Down syndrome. Our central hypothesis is that successful completion of the Strider “Learn to Ride” intervention will provide children with Down syndrome the ability to ride a two-wheel balance bike safely and independently. We also hypothesize that balance biking will be a sustainable activity that has the potential to greatly increase the functional balance, participation, and physical activity levels of youth with Down syndrome because we propose riding Strider bikes to be enjoyable and motivating for this population.

SPECIFIC AIM(S)	
Page 4 of 74/5/2019 Specific Aim(s) We plan to test our central hypothesis and meet our overall objective for this project by pursuing the following specific aims: 1. Determine the ability of youth with DS to learn to ride a Strider balance bike, within one week, utilizing the Strider “Learn to Ride” curriculum. Our working hypothesis is that youth with DS who complete the five “Learn to Ride” classes will be able to successfully and safely ride their Strider bike 100’ or more without loss of balance. 2. Determine the efficacy of balance biking on improving balance in youth with DS, as measured by the Pediatric Balance Scale (PBS). Our working hypothesis that balance will be improved in youth with DS who complete the balance biking intervention because biking is an enjoyable childhood PA that requires high levels of postural control. 3. Determine the long-term sustainability of balance biking for youth with DS, as estimated by a 3-, 6-, 9-, and 12-month follow up surveys. Our working hypothesis here is that balance biking will be a sustainable form of PA for individuals with DS that can be continued throughout the lifespan, leading to increased PA levels and decreased time spent engaged in sedentary behaviors. 4. Determine the impact of long-term participation in balance biking on home, school, and community participation levels, as measured by the Participation and Environment Measure for Children and Youth (PEM-CY). Our working hypothesis that long-term involvement in a balance biking program will lead to increased participation in home, school, and community environments.

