STUDY DESIGN	
The proposed pilot study is a pre-post-test design with each participant serving as his or her own control. The proposed study design will provide preliminary data towards answering the hypothesis and specific aims. Children ages 5-17 years old with a diagnosis of Down syndrome will be recruited to participate from pediatric therapy clinics, schools, and the Central Mississippi Down Syndrome Association. Each participant will be provided with a Strider balance bike to use for the intervention. On the first day of the intervention, each participant will complete the Pediatric Balance scale and the distance that each child can cycle will be recorded. Participants’ parents will be asked to complete the Participation and Environment Measure for Children

	and Youth (PEM-CY) and the PROMIS physical activity questionnaire on the first day of the intervention. Each participant will complete the 5-day Strider Learn to Ride Intervention under the supervision of a physical therapist. On the last day, each child will be reassessed with the Pediatric Balance Scale and the distance that each participant can cycle will again be recorded. Participants' caregivers will be contacted by mail from the PI to complete follow up outcome measures (PEM-CY and PROMIS questionnaire) at 3-and6-months.
INCLUSION CRITERIA	To be included in the study, the individuals must 1) be between the ages of 5 and 17 years old with a diagnosis of Down syndrome, 2) have the core strength and balance necessary to maintain sitting on a two-wheel bike with their feet on the ground, and 3) be able to follow simple commands.
EXCLUSION CRITERIA	The exclusion criteria for the study are 1) significant cardiovascular event or illness in the past 6 months and 2) another medical diagnosis, besides Down syndrome, that would limit participation in the biking intervention.
NUMBER OF SUBJECTS	Approximately 10 participants will be recruited to participate in the pilot study, based on the recommended number of participants for each Strider "Learn to Ride" intervention.

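### Aim 4 claims to determine the impact of long-term balance biking, but the plan delivers a five-day course and names no measure of later riding, so follow-up can only describe change after the course

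*Combined protocol and SAP*

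**What the plan says.** The combined protocol and SAP describes the long-term question in two ways.

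- **Specific Aim(s), Aim 4** makes continued riding the exposure: "Determine the impact of long-term participation in balance biking on home, school, and community participation levels". Its working hypothesis is that "long-term involvement in a balance biking program will lead to increased participation in home, school, and community environments".
- **The Abstract** names a different exposure: "the long-term effects of completion of the intervention on the participation and physical activity levels of children with DS". The **Purpose** uses the same idea ("the long-term effects of completion of" the intervention), and **Study Endpoints** speaks of long-term outcomes associated with the intervention.

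On delivery, **Study Design** says "Each participant will complete the 5-day Strider Learn to Ride Intervention under the supervision of a physical therapist" and, on equipment, "Each participant will be provided with a Strider balance bike to use for the intervention". No later sessions, home riding plan, or loan or gift of the bike is described. Nor is any return of the bike.

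On follow-up, caregivers are to "complete follow up outcome measures (PEM-CY and PROMIS questionnaire) at 3-and6-months", by mail. **Outcome Measures** adds that this follow-up will also assess sustainability, but names no item on bike access or riding frequency. **Statistical Methodology** gives paired t-tests, with a Wilcoxon fallback, for pre- and post-test PEM-CY scores. It does not mention riding status. Each child is his or her own control.

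**The concern.** The exposure in Aim 4 and its hypothesis is neither delivered nor named as something to be measured. The planned PEM-CY comparison pools all children, whether or not they rode after day 5.

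What is at stake is the conclusion. A flat PEM-CY at 6 months could mean that continued riding does not help, or that few children continued to ride. A rise could come from riding, from the course itself, or from growth, season and other activities. Under the present wording of Aim 4, either result could be reported as evidence about long-term riding. The Background lists the cost of adaptive equipment among the barriers to activity in this population, so lack of a bike after the course is a possibility that the plan itself raises.

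**Working it through.** The plan has no figure to reproduce. It gives no alpha, power, effect size or SD, and the sample size rests on the recommended class size. The point is settled by reading; the arithmetic only shows scale.

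**1. Target against delivery**

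| Section | Exposure named or delivered |
|---|---|
| Aim 4 and its hypothesis | Long-term riding; long-term involvement in a programme |
| Abstract, Purpose | Completion of the intervention |
| Study Endpoints | Outcomes associated with the intervention |
| Study Design (delivered) | Five supervised days; bike access afterwards not stated |
| Study Design, Outcome Measures (measured later) | PEM-CY and PROMIS; no riding item named |

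The design matches the second and third rows, not the first.

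**2. What the pooled change contains**

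Write the mean change from baseline to follow-up as D = g + c + f × r, where

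- g is the change that would have happened anyway,
- c is the effect of having taken the course, whatever happens later,
- f is the share of children still riding,
- r is the effect of continued riding in those who ride.

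The study observes D alone. With no control group, g cannot be separated from the rest. With no riding item, f is unknown. D = 0 is compatible with r > 0 if f is small, and D > 0 is compatible with r = 0. D does describe change after the course, which is what the Abstract and Purpose ask about.

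**3. Illustration of scale**

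Inputs from the Background, both from a different bike programme: 44% did not learn to ride in one study, so 56% did; 61% of children with DS kept riding at home in another. If 61% applies to all children, f = 0.61. If it applies only to those who learned, f = 0.56 × 0.61 = 0.34. Sample size is about 10 (Number of Subjects) or 20 (Abstract).

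Assumptions, none of them in the documents: two-sided alpha 0.05, 80% power if everyone rides, g = c = 0, and the SD of change held fixed. The standardised change is mean change divided by the SD of change. Power is from the exact paired t-test (noncentral t).

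| N | f | Expected riders | Whole-group standardised change | Power |
|---|---|---|---|---|
| 10 | 1 | 10 | 1.00 | 80% |
| 10 | 0.61 | 6.1 | 1.00 × 0.61 = 0.61 | 40% |
| 10 | 0.34 | 3.4 | 1.00 × 0.34 = 0.34 | 16% |
| 20 | 1 | 20 | 0.66 | 80% |
| 20 | 0.61 | 12.2 | 0.66 × 0.61 = 0.40 | 40% |
| 20 | 0.34 | 6.8 | 0.66 × 0.34 = 0.23 | 16% |

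A null result would therefore say little about r, even if r were large.

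**The case against.** The strongest reply has four parts.

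- **Bike supply.** A reader might infer that the bikes go back on day 5, so that the plan rules out later riding. The documents do not support this. The Study Design sentence states what the bike is for, not when it is returned. Aim 1 and Outcome Measures refer to the bike as the child's own, which leaves the matter open. Consent pages, where such a term might stand, were not available for review. The Background also describes the bikes as commercially available. This part of the reply stands: bike access is unstated, not denied.
- **Aim 3.** A reader might extend the criticism to "Determine the long-term sustainability of balance biking for youth with DS, as estimated by a 3-, 6-, 9-, and 12-month follow up surveys". But continuing after supervised classes end is what sustainability means, and whether families obtain and use a bike is arguably part of the answer. This also stands. What Aim 3 lacks is a named measure of riding.
- **Short training, long follow-up.** The Background cites a five-day programme with possible activity effects for up to 12 months, so the schedule is a reasoned choice. Setting 5 days of training against about 180 days of follow-up (2.8%) would mislead, because a learned skill is not used up on day 5. Accepted.
- **Pilot status.** Study Design promises only preliminary data, and no section says how a null would be read. This limits the seriousness, but Aim 4 and its hypothesis still state an effect of long-term riding.

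The reply does not supply a programme beyond five days, a riding measure or a control group. The mismatch in Aim 4 remains.

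**Conclusion.** The point holds for Aim 4. As worded, that aim cannot be answered by the planned data: the pooled, uncontrolled change in PEM-CY supports neither an effect nor an absence of effect of long-term riding. The same data can describe change after the five-day course.

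This conclusion rests on the text alone. The fall in power from 80% to about 16% to 40% is an illustration. It borrows continuation figures from another programme and assumes no change in non-riders. If the course itself changes participation, the whole-group change would be larger, but it would then be even less attributable to riding.

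The documents do not support the stronger statement that children have no bike after day 5, nor that Aim 3 is unanswerable in principle. For a pilot this should be corrected before results are reported. It does not undermine the immediate balance and distance outcomes.

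**What to change.** **Preferred.** Reword Aim 4 and its hypothesis to *change in participation after completion of the five-day Learn to Ride intervention*. Add one sentence to Statistical Methodology: neither a rise nor a null at 3 or 6 months will be interpreted as evidence about long-term riding. This costs no data; the downside is a narrower claim.

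**If the long-term wording is kept.** State in Study Design whether children have the bike through the last follow-up. Add a caregiver item on bike access and riding frequency to the forms already being mailed. Describe PEM-CY and PROMIS change by riding status. This costs one or two survey items. The comparison would remain descriptive: on the illustrative shares there would be only about 3 to 6 riders among 10 children, riders may differ in family resources and motivation, and there is still no control group.

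**Aim 3.** The sustainability question can stand, with the same access and riding item added so that its answer can be interpreted. While editing, reconcile its follow-up times (3, 6, 9 and 12 months) with the 3 and 6 months in Study Design, Outcome Measures and Study Endpoints.

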OUTCOME MEASURES	Outcome measures used will include the Pediatric Balance Scale (PBS), distance cycled, Participation and Environment Measure for Children and Youth (PEM-CY), and PROMIS questionnaire. The PBS is a valid, 14-item assessment, developed based on the Berg Balance Scale. The PBS is a criterion-based measure, with each item scored on a 0-4 scale. Distance cycled will be measured based on the longest straight-line distance, out of three trials, that the participant is able to safely and independently propel their Strider bike. The PEM-CY is a participation level outcome measure used to assess a child's engagement in activities in the home, school, and community environments. The PEM-CY is a valid and reliable measure and is completed by parent/caregiver report, making it appropriate to use with children with Down syndrome. The final outcome measure, a parent report PROMIS questionnaire to assess PA levels of participants, will also be used. Long-term follow up at 3-and 6 months, through mail, will be completed to assess long-term changes in participation and physical activity levels as well as the sustainability of the Strider bike intervention for this population.
STUDY ENDPOINTS	All outcomes measures will be administered on the first day of the intervention to collect pre-intervention data. Upon completion of the five-day "Learn to Ride" intervention, the Pediatric Balance Scale and distance cycled will again be administered for post-intervention data. The Participation and Environment Measure for Children and Youth and the PROMIS physical activity questionnaire will be administered, my mail, to each participants' caregiver/parent at 3-and-6-months following completion of the

	
intervention to assess long-term outcomes associated with the intervention.

STATISTICAL METHODOLOGY	
IMB SPSS Statistics will be used to analyze all data. Dependent t-tests will be used to analyze pre-and post-test scores of the Pediatric Balance Scale, Participation and Environment Measure for Children and Youth, and distance cycled. If assumptions are not met, a Wilcoxon Signed Ranks test will be used to analyze the data.

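### The planned sample size is stated as an estimated 20 in the Abstract and as approximately 10 in Number of Subjects, and nothing reconciles the two

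*Combined protocol and SAP*

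**What the plan says.** Two sections of the combined protocol and SAP give the number to be recruited.

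- **Abstract:** "An estimated 20 children between the ages of 5 and 17 years old will be recruited". No basis is given.
- **Number of Subjects:** "Approximately 10 participants will be recruited to participate in the pilot study, based on the recommended number of participants for each Strider" (the programme's name follows). The basis is class size.

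Three further points bear on how the numbers can be read.

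- **Study Design** describes a "pre-post-test design with each participant serving as his or her own control", so there is one group.
- **Study Design** also says: "Each participant will complete the 5-day Strider Learn to Ride Intervention under the supervision of a physical therapist". It does not say how many classes will be run.
- **Statistical Methodology** says: "Dependent t-tests will be used to analyze pre-and post-test scores of the Pediatric Balance Scale", and applies the same test to the participation measure and distance cycled, with a Wilcoxon signed-rank test as fallback. It gives no significance level, power, effect size, SD or dropout rate.

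**The concern.** Both figures are current text, and both concern recruitment to the same study. One is twice the other, which is more than words such as *estimated* and *approximately* can cover.

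The plan contains no power or precision calculation, so the stated count is all that defines when recruitment is complete. If 10 children are enrolled, one section shows the target met and the other shows it missed by half. If 20 are enrolled, one shows it met and the other shows it doubled. Resources are affected too, because each child receives a bike to use and a supervised five-day course. On the protocol's own class-size rationale, 10 children are one class and 20 are two. The precision of every planned paired comparison also depends on which number is meant.

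**Working it through.** **Is there a stated calculation to reproduce?** No. The figure of 10 rests on class size and the figure of 20 has no stated basis. The check is therefore whether the text allows one number to be derived from the other.

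| Possible reconciliation | What the text says | Result |
|---|---|---|
| Two classes of 10 | Number of Subjects takes the recommended size of one class but sets it as the number for the whole pilot study. No section mentions a second class. | Not supported |
| Two arms of 10 | Study Design has each child as his or her own control. | Ruled out |
| 20 recruited, 10 evaluable | Both sections speak of recruitment. It would need 50% loss, 20 × (1 − 0.5) = 10, and no dropout rate is stated. | Not supported |
| One figure superseded | No amendment or rule of precedence is given. | Not supported |

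**What the difference does to the planned paired t-test.** The documents state none of the following, so they are assumptions: two-sided 5% level, normally distributed differences and, except where noted, no dropout. Results are in units of the SD of the within-child differences, because no SD is given.

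The 95% confidence interval half-width for the mean change is t(0.975, n − 1) / √n:

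- n = 10: 2.262 / 3.162 = 0.715 SD
- n = 20: 2.093 / 4.472 = 0.468 SD
- ratio: 0.715 / 0.468 = 1.53

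If one fifth of the children are not retested (an assumed rate), 8 or 16 are analysed:

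- n = 8: 2.365 / 2.828 = 0.836 SD
- n = 16: 2.131 / 4 = 0.533 SD

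Power comes from the noncentral t distribution with n − 1 degrees of freedom and noncentrality d√n, where d is the true mean change divided by the SD of the differences:

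| Quantity | n = 10 | n = 20 |
|---|---|---|
| Change detectable with 80% power | 0.996 SD | 0.660 SD |
| Power at d = 0.5 | 29% | 56% |
| Power at d = 0.8 | 62% | 92% |
| Power at d = 1.0 | 80% | 99% |

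The Wilcoxon fallback, simulated with normal differences at d = 0.8, has power of about 60% with 10 children and 91% with 20, so the contrast does not depend on which test is used.

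**The case against.** The strongest reply is that little turns on this. Neither number enters a stated calculation, no interim look or stopping rule depends on it, and the paired test is carried out in the same way with 10 or 20 children. The sample size changes precision, not validity, and the study is openly a pilot. That is correct, and it limits the consequence to the recruitment target, resources and precision.

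A second reply is that the text has a natural hierarchy. Number of Subjects is the dedicated section and the only one that gives a reason, while the Abstract is a summary and calls its figure an estimate. A reader might reasonably take 10 as operative. This makes 10 the more likely reading but does not settle it. The plan states no precedence, and the class-size reason could equally lie behind a plan for two classes totalling 20.

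A third reply is that the power figures rest on assumed inputs, that no planned power is lost because none was planned, and that results in SD units cannot be read as points on the balance scale. All of this stands. The figures illustrate the consequence and do not check anything the plan claims. What the documents themselves establish is the twofold difference. For the same reason, the point is better described as an internal inconsistency than as an arithmetic error.

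**Conclusion.** The concern holds. The plan gives two recruitment targets, 20 and about 10, for the same single-group study, and no reading of the text reconciles them. The factor of two comes directly from the documents and needs no assumption. The consequence for the paired comparisons does rest on the assumptions set out above: a confidence interval about one and a half times as wide with 10 children as with 20, and a detectable change of about 1 SD rather than about two thirds of an SD. The documents do not show which number is right, and this review does not presume to. A pilot does not need a formal power calculation, but it does need one planned size, so the conflict must be resolved.

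**What to change.** State one number in both sections.

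- If one class is intended, change the Abstract to approximately 10 children.
- If two classes are intended, change Number of Subjects to approximately 20 participants, in two Learn to Ride classes of about 10.

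It would help, though the contradiction does not require it, to give beside the chosen number the precision it delivers, with the assumptions named, and to describe the balance result as a pilot estimate at that precision.

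The cost is a wording correction in one section, with no new analysis. There are two possible downsides. The stated size or precision may look less favourable. And if 20 is the real target but only one class was resourced, a second five-day class will be needed.

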	
low fitness levels of this population. Identification of enjoyable, sustainable, accessible, and effective forms of PA for this population is necessary in order to promote improved overall health and participation across the lifespan. Bicycle riding has been identified as a source of moderate to vigorous PA for children and adolescents and is a noncompetitive, highly accessible activity that can be enjoyed across the lifespan. However, research examining bike riding as an enjoyable and effective PA intervention for adolescents with developmental disabilities, particularly DS, is limited. One study examined the benefits of children with DS learning to ride an adaptive two-wheel bicycle. The children participated in “Lose the Training Wheels”, an intensive, five-day program aimed at teaching the skill of riding a two-wheel bike independently. Specially designed two-wheel adaptive bikes were used for initial training. The bikes were modified to include a push handle on the back, to be used by the instructor, and rear roller wheels to increase the bike’s base of support. Forty-four percent of the participants were unable to learn to ride a two-wheel bike during the training period. However, children who did complete the training program decreased their time spent in sedentary behavior by 75 minutes per day, indicating that new motor skill development might positively impact PA levels for up to 12 months following the initial intervention period. A similar study also examined the effectiveness of the “Lose the Training Wheels” program, previously described, for children and adolescents with DS and Autism Spectrum Disorder. The results indicated that 61% of children with DS continued to ride their bike at home after the intervention period ended, supporting transfer of an enjoyable PA to the natural environment. However, the adaptive bikes used for the “Lose the Training Wheels” program are specially made and not commercially available, making widespread access to this intervention difficult. Strider Bikes, a brand of commercially available balance bikes, are specifically designed to be lightweight, easy to handle, and safe for use with children with disabilities. One study using Strider bikes reported that children with autism spectrum disorder demonstrated significant improvements in postural control following completion of 15 minutes of riding, three days per week for five weeks. However, there is currently no research available that has utilized Strider bikes with youth with DS. In order to impact a large population of children with DS and create lasting, positive outcomes, a relatively inexpensive, commercially available adaptive bike and effective instructional intervention must be identified.

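### No listed outcome is described as recording balance biking after the five-day course, so the sustainability part of Aim 3 has no named variable, criterion or analysis; PROMIS, the only physical activity measure, is also missing from the test list

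*Combined protocol and SAP*

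**What the plan says.** Aim 3 in Specific Aim(s) is to "Determine the long-term sustainability of balance biking for youth with DS, as estimated by a 3-, 6-, 9-, and 12-month follow up surveys". Its working hypothesis adds that physical activity will rise and sedentary time will fall. Outcome Measures repeats the sustainability purpose, saying that the mailed follow-up is "completed to assess long-term changes in participation and physical activity levels as well as the sustainability of the Strider bike intervention for this population".

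The instruments for that follow-up are named in Study Design, where caregivers are to "complete follow up outcome measures (PEM-CY and PROMIS questionnaire) at 3-and6-months". Study Endpoints names the same two. Outcome Measures describes PEM-CY as a measure of engagement at home, at school and in the community, and PROMIS as "a parent report PROMIS questionnaire to assess PA levels of participants".

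The one outcome that concerns riding is distance cycled, the longest of three straight-line trials. It is taken on the first day, and at the end of the course "the Pediatric Balance Scale and distance cycled will again be administered for post-intervention data". No later measurement is planned.

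Statistical Methodology uses dependent t-tests, with a Wilcoxon signed-rank fallback, to "analyze pre-and post-test scores of the Pediatric Balance Scale, Participation and Environment Measure for Children and Youth, and distance cycled".

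Aim 4 is to "Determine the impact of long-term participation in balance biking on home, school, and community participation levels", using PEM-CY.

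**The concern.** Sustainability of balance biking means, at the least, whether children go on riding. The protocol treats that as a result worth knowing: the Background reports from a similar programme that "61% of children with DS continued to ride their bike at home after the intervention period ended". A team following this plan could report PROMIS and PEM-CY changes at 3 and 6 months and still be unable to say how many children were riding. Unless a returned form happened to ask, this could not be repaired at the analysis stage; later recall would be the only source.

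The PROMIS omission is different in kind. Those data are collected on day 1 and at follow-up, so nothing is lost, but the part of Aim 3 that is measured has no stated test.

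**Working it through.** The plan states no figure on this point, so there is none to reproduce. The main check sets each listed outcome against Aim 3.

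**Step 1. Outcomes, timing and tests** (Study Design, Outcome Measures, Study Endpoints, Statistical Methodology)

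| Outcome | Described as measuring | When | In test list |
|---|---|---|---|
| Pediatric Balance Scale | balance | first and last course day | yes |
| Distance cycled | riding skill, best of three trials | first and last course day | yes |
| PEM-CY | participation | day 1, 3 and 6 months | yes |
| PROMIS | physical activity level | day 1, 3 and 6 months | no |

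Of the four outcomes, none is described as recording riding after the last course day. No criterion for sustained riding and no analysis of it is given. Three of the four outcomes are in the test list; the missing one is the only physical activity measure. The statement that SPSS will analyse all data names software, not a method.

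Activity level cannot stand in for riding. It can rise in a child who has stopped riding, and a child can ride without a measurable change in it.

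**Step 2. What a riding item would deliver**

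Inputs: n = 10 (Number of Subjects) and n = 20 (Abstract), both shown because the two sections differ; 61% (Background), for illustration only. The other counts are assumptions.

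Exact (Clopper-Pearson) 95% limits for x of n: the lower is the 0.025 quantile of Beta(x, n − x + 1), the upper the 0.975 quantile of Beta(x + 1, n − x).

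- n = 10: 0.61 × 10 = 6.1, so 6/10 = 60%, limits 26.2% to 87.8%.
- n = 20: 0.61 × 20 = 12.2, so 12/20 = 60%, limits 36.1% to 80.9%.
- Assumed non-return, n = 10 with 8 packets back and 5 children riding: if both non-returners are not riding, 5/10 = 50% (18.7% to 81.3%); if both are riding, 7/10 = 70% (34.8% to 93.3%).
- Assumed day-1 riders, 2 of 10, with 6 riding at follow-up including both: among the other 8, 4/8 = 50% (15.7% to 84.3%). The inclusion and exclusion criteria do not rule out children who already ride.

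**Step 3. PROMIS change**

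The 95% half-width, in standard deviations of the change, is t(0.975, n − 1)/√n:

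- n = 10: 0.72
- n = 8 (assumed, two packets not returned): 0.84
- n = 20: 0.47

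Steps 2 and 3 show the precision of the remedy. They do not measure the size of the gap.

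**Step 4. Aim 4**

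PEM-CY is measured and is in the test list. The exposure that the aim names, long-term participation in biking, is not among the listed outcomes. Study Design describes one group, each child serving as his or her own control. Change over months in growing children would therefore not be attributable to biking even if riding were recorded.

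**The case against.** The best reply is that the riding data may be collected after all. Aim 3 relies on follow-up surveys, the Abstract mentions a parent-report questionnaire, and the items of neither are shown. This stands in part. A reader might infer from the plan that no riding data will be gathered; the documents do not support so flat a statement, because an incidental item cannot be excluded. But Study Design and Study Endpoints identify the mailed forms as PEM-CY and PROMIS, and an incidental item would still not be a named endpoint with a criterion and an analysis.

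A second reply is that this is a pilot for preliminary data, and its central hypothesis, the ability to ride safely and independently, is served by distance cycled, which is in the test list. That is fair and limits the severity: Aims 1 and 2 are untouched. The PROMIS omission may be a drafting slip, repaired by adding it to one sentence.

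A third is that a proportion from about 10 children says little. It is imprecise, but it is more than the plan now provides.

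Finally, a reader might infer that recording riding would let a PEM-CY change be credited to long-term biking. It would not, for the reason in Step 4. Rewording Aim 4 as the effect of completing the course would still be a causal claim.

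**Conclusion.** The point holds in this form: sustainability is a stated aim and a stated purpose of the follow-up, but it has no named variable, criterion or analysis, and PROMIS has no stated test. The plan as written specifies nothing that would yield an estimate of continued riding at any follow-up. That is the size of the gap; the intervals above only show that the remedy would be descriptive.

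The conclusion rests on how the plan describes its instruments, not on their items, which the documents do not give. The 61% is context, not a benchmark: it comes from a different programme, and its criterion and timing are not stated.

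The change should be made before data collection, because missing riding data could not be recovered at analysis. Two related points are minor: sedentary time in Aim 3 has no named measure, and Aim 3 lists 3, 6, 9 and 12 months where Study Design, Outcome Measures and Study Endpoints list 3 and 6.

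**What to change.** 1. Add parent-report items to the day-1 forms and each mailed packet: current access to a balance bike; days in the past 30 on which the child rode a balance bike; and days on which the child rode a pedal two-wheel bike. Access matters because Study Design provides a bike for the intervention and does not say whether families keep it.
2. Prespecify a criterion for still riding, chosen and justified by the investigators. Report balance-bike riding as the Aim 3 figure and riding of either bike beside it, so that moving on to a pedal bike is not read as stopping. Also give the distribution of days ridden.
3. At each follow-up, report each proportion with an exact 95% interval, all enrolled children as denominator, the number of packets not returned, and bounds counting non-returners as all not riding and as all riding. Give the same proportion among children not riding on day 1. Label these results descriptive.
4. Add PROMIS change from day 1 to each follow-up to the paired analyses: mean change, 95% interval and the same Wilcoxon fallback.
5. Word Aim 4 as change in PEM-CY after completing the intervention, with no causal claim. Any breakdown by riding status is descriptive only.
6. Delete the sedentary-time clause or add a measure for it, and reconcile the follow-up times across sections.

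The cost is a few short items on forms already in use, one more outcome in the paired analyses and a minor amendment. The downsides are recall error, a slightly longer form that could lower returns a little, one more comparison per follow-up, and wide intervals.
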